Appendix D10b: Exploratory Bayesian analysis for lactate clearance	43

1. Introduction

This document is the Statistical Analysis Plan (SAP) for the RePHILL trial, and should be read in conjunction with the current trial protocol. This SAP details the proposed analyses and presentation of the data for the main paper(s) reporting the results for the RePHILL trial.

The results reported in these papers will follow the strategy set out here. Subsequent analyses of a more exploratory nature will not be bound by this strategy, though they are expected to follow the broad principles laid down here. The principles are not intended to curtail exploratory analysis (e.g. to decide cut-points for categorisation of continuous variables), nor to prohibit accepted practices (e.g. transformation of data prior to analysis), but they are intended to establish rules that will be followed, as closely as possible, when analysing and reporting data.

Any deviations from this SAP will be described and justified in the final report or publication of the trial (using a table as shown in Appendix A). The analysis will be carried out by an appropriately qualified statistician, who should ensure integrity of the data during their data cleaning processes.

2. Background and rationale

The background and rationale for the trial are outlined in detail in the protocol. In brief, the administration of high ratios of plasma to packed red blood cells (PRBC) has been widely adopted for in-hospital treatment of major traumatic haemorrhage. Acceptance of in-hospital haemostatic resuscitation saw the British military implement it for battlefield casualty retrieval. With the increasing adoption of giving Pre-Hospital Blood Products (PHBP) for trauma in both the UK and abroad, in both military and civilian settings, it is important to determine whether this intervention is effective. The provision of PHBP requires considerable logistical and financial resources and RePHILL will establish a high quality evidence base for PHBP resuscitation.

3. Trial objectives

The primary objective is to investigate the clinical effectiveness of PHBP resuscitation compared to the current standard care of restricted crystalloid based resuscitation in participants suffering from major traumatic haemorrhage.

Secondary objectives are to test the hypotheses that, when compared to standard care, does PHBP resuscitation:

- I. Improve blood pressure, heart rate and capillary oxygenation on Emergency Department (ED) arrival?
- II. Prolong on-scene time?
- III. Reduce pre-hospital fluid requirements?
- IV. Reduce in-hospital transfusion requirements?

- V. Reduce trauma-induced coagulopathy?
- VI. Preserve platelet function?
- VII. Lead to a greater incidence of transfusion-related complications, particularly acute respiratory distress syndrome (ARDS)?
- VIII. Lead to blood product wastage?
- IX. Affect haemoglobin concentration levels on ED arrival?

4. Trial methods

4.1. Trial design

RePHILL is a multi-centre, prospective, open-label, superiority, parallel group, phase III randomised controlled trial with an internal pilot phase See Appendix B for trial schema The progression rules for the internal pilot are described in section 4 10

Participants will be recruited at the scene of their traumatic injury

4.2. Trial interventions

PHBP (Lyophilised Plasma LyoPlas N-w (LyoPlas) and PRBC) resuscitation vs crystalloid (0.9% sodium chloride [normal saline]) resuscitation (standard care)

4.3. Primary outcome measure

The primary outcome is a composite measure consisting of episode mortality (mortality between time of injury/recruitment and discharge from the primary receiving facility to non-acute care) and lactate clearance An event is defined as either episode mortality or a failure to achieve lactate clearance of $\geq 20\%$ per hour in the first 2 hours after randomisation where a participant is considered randomised and entered into the trial when the first intervention box has been opened

4.4. Secondary outcome measures

Secondary outcomes are as follows:

- Individual components of the primary outcome
- All-cause mortality within 3 hours of randomisation
- All-cause mortality within 30 days of randomisation
- Pre-hospital time and type and volume of fluid
- Vital signs (systolic blood pressure, heart rate, capillary oxygen saturation) at scene, on arrival at the ED, then also at 2, 6, 12 and 24 hours after arrival at ED
- Haemoglobin concentration on ED arrival

- (Venous) lactate concentration on arrival at ED and at 2 hours after arrival at ED
- Trauma-induced coagulopathy (defined as International Normalised Ratio (INR) >1.5) to be measured on arrival at ED, and also at 2 and 6 hours after arrival at ED
- Total blood product receipt at 6, 12 and 24 hours after arrival at ED
- ARDS within the first 7 days after injury
- Transfusion-related complications
- Organ failure-free days The presence of organ failure is defined as any Sequential Organ Failure Assessment (SOFA) component score of ≥ 3 . Organ failure will be assumed to be absent if the participant is discharged from acute care and will be assumed to be present if the participant has died

At selected receiving hospital sites (RHS) the following secondary outcomes will also be recorded:

- Coagulation measured viscoelastically by rotational thromboelastometry (ROTEM[®])
- Platelet function using multiple electrode impedance aggregometry (MultiPlate)

4.5. Timing of outcome assessments

The schedule of trial procedures and outcome assessments are given in the protocol. Secondary outcome measures will be assessed on at least one of the following time points: on-scene; 3 hours post randomisation; arrival at ED; 2, 6, 12, and 24 hours after arrival at ED; and daily assessments up to day 30.

4.6. Randomisation

Participants will be randomised at the level of the individual in a 1:1 ratio to either PHBP (Lyophilised Plasma LyoPlas N-w (LyoPlas) and PRBC) resuscitation or crystalloid (0.9% sodium chloride [normal saline]) resuscitation.

Randomisation will be performed centrally at the Birmingham Clinical Trials Unit (BCTU) using stratification by intervention delivery site (IDS) to account for variation in trauma care and type of trauma between delivery sites.

In the RePHILL trial, the blood banks will maintain a constant supply of randomised trial interventions to the Pre-Hospital Emergency Medical (PHEM) team. The blood bank will obtain the randomised allocations via a secure online system at the BCTU.

Blood banks will be supplied with pre-printed 'treatment box number' labels. A registered user at the blood bank will request a treatment allocation from the BCTU and will receive a treatment box number and treatment arm allocation. The allocated trial intervention will be packed into transport boxes affixing the correct labels. Transport boxes will be issued as a pair, one marked red and one marked yellow per single randomised allocation. The packed, sealed transport

boxes will be dispatched to the PHEM base using an established courier service as required

On-scene, the PHEM doctor will assess the potential participant's vital signs on scene and confirm if eligible for entry into the RePHILL trial. If they fulfil the eligibility criteria for the trial, the randomised treatment will be given. Participants are considered randomised into the trial when the PHEM team open the first transport box containing the allocated trial intervention.

4.7. Sample size

Although no definitive data exists on the composite primary outcome measure, observational studies suggest potentially dramatic reductions in mortality from civilian pre-hospital PRBC¹ and military pre-hospital PRBC with thawed plasma². Following extensive consultation with experts in pre-hospital trauma resuscitation, it is considered that an absolute reduction of 10% in the proportion of participants experiencing one of the component primary outcomes is clinically meaningful for the participants and is an appropriate effect size upon which to base the power calculation.

To detect an absolute difference of 10% between groups in the proportion of participants experiencing either episode mortality or lactate clearance $<20\%/h$ in the two hours post-randomisation (i.e. from 20% in the standard care group to 10% in the group receiving PHBP) using the method of difference between proportions (2-sided Fisher's Exact Test) with 80% power, and a type 1 error rate of 5% (i.e. $\alpha=0.05$), requires 219 participants per group to be randomised, 438 participants in total. Assuming and adjusting for a 10% loss to follow-up rate, 490 participants will need to be recruited.

The interim analysis for the Data Monitoring Committee (DMC) meeting in May 2018 reported the results on the 192 participants recruited by 20th April 2018. A pooled event rate of 65% experiencing either episode mortality or lactate clearance $<20\%/h$ in the two hours post-randomisation was observed in these participants. This observed rate does not correspond with the pooled event rate of 15% assumed in the original sample size calculations. On the DMC's recommendations, this issue was discussed with the TSC in October 2018. The TSC recommended that the power calculations were framed in terms of a relative risk rather than an absolute risk, with the original target sample size of 490 unchanged.

Assuming the pooled event rate remains at 65% and allowing for a 10% loss to follow-up rate, 490 participants will provide 80% power to detect a relative risk ratio of 0.82 (i.e. from 71.7% in the standard care group to 58.3% in the group receiving PHBP) using the method of difference between proportions (2-sided Fisher's Exact Test), and a type 1 error rate of 5% (i.e. $\alpha=0.05$). This estimated relative risk ratio is consistent with the relative risk ratios of 1.54³ and 0.70⁴ reported in two recent pre-hospital randomised controlled trials using plasma in one of the treatment arms.

4.8. Framework

The objective of the trial is to test the superiority of one intervention to another

The null hypothesis is that there is no difference in the composite outcome of either episode mortality or a failure to achieve lactate clearance $\geq 20\%$ per hour in the first 2 hours after randomisation between the intervention groups. The alternative hypothesis is that there is a difference between the groups.

4.9. Interim analyses and stopping guidance

A separate DMC reporting template will be drafted and agreed by the DMC including an agreement on which outcomes will be reported at interim analyses. The statistical methods stated in this SAP will be followed for the outcomes included in the DMC report, where possible.

If PHBP resuscitation is substantially better or worse than crystalloid resuscitation with respect to the composite outcome of episode mortality or lactate clearance, then this may become apparent before the target recruitment has been reached. Alternatively, new evidence might emerge from other sources to suggest that PHBP resuscitation is definitely more, or less, effective than crystalloid resuscitation. To protect against any unnecessary continuation of the trial, interim analyses of major endpoints and safety data will be supplied, in strict confidence, to the independent DMC, along with updates on results of other related studies, and any other analyses that the DMC may request.

The DMC will advise the chair of the Trial Steering Committee (TSC) if, in their view, any of the randomised comparisons in the trial have provided both: a) "proof beyond reasonable doubt" that for all, or for some, types of participant one particular intervention is definitely indicated or definitely contra-indicated in terms of a net difference of a major endpoint; and b) evidence that might reasonably be expected to influence the patient management of many clinicians who are already aware of the other main trial results. Unless this happens, however, the TSC, the collaborators and all of the central trial staff (except the statisticians who supply the confidential analyses) will remain unaware of the interim results.

^t Appropriate criteria of proof beyond reasonable doubt cannot be specified precisely, but a difference of at least $p < 0.001$ (similar to a Haybittle-Peto⁵ stopping boundary) in an interim analysis of a major endpoint may be required to justify halting, or modifying, the study prematurely. If this criterion were to be adopted, it would have the practical advantage that the exact number of interim analyses would be of little importance, so no fixed schedule is proposed. Given the proposed use of the Haybittle-Peto boundary, no adjustment for multiple testing (to control the overall type I error rate) is proposed, i.e. the threshold for statistical significance at the final analysis will still be $p = 0.05$.

4.10. Internal Pilot Progression Rules

The first 6 months of the RePHILL trial will constitute an internal pilot to assess and confirm the trial logistics to determine if it is both feasible and practical to carry on and recruit into the trial. The pilot will be run at multiple sites to validate the multi-centre aspects of the trial.

At the end of the pilot phase, the following targets should be met to justify progression to the main trial:

- Minimum of 25 participants recruited across at least two active sites;
- In participants recruited to the trial intervention arm, at least one unit of PRBC and one unit of LyoPlas delivered to at least 80% of participants before reaching hospital;
- At least 90% complete data capture;
- DMC reports no safety concerns, which would prohibit continuation to main trial.

The pilot data was reviewed by the DMC and TSC on 26/APR/2017 and the trial was allowed to continue.

4.11. Timing of final analysis

The final analysis for the trial will occur once all the participants have completed the trial. The main trial data collection for participants ends at withdrawal, discharge to non-acute care, death or at 30 days follow-up, whichever occurs first. Apart from episode mortality data which is collected up to discharge from acute care which may be >30 days. Final analysis will then occur only after the corresponding outcome data has been entered onto the trial database and validated as being ready for analysis. This is provided that the trial has not been stopped early for any reason (e.g. DMC advice or funding body request).

4.12. Timing of other analyses

Not applicable

4.13. Trial comparisons

All references in this document to 'group' refer to PHBP (Lyophilised Plasma LyoPlas N-w (LyoPlas) and PRBC) or crystalloid (0.9% sodium chloride [normal saline]) resuscitation.

5. Statistical Principles

5.1. Confidence intervals and p-values

All estimates of differences between groups will be presented with two-sided 95% confidence intervals, unless otherwise stated. P-values will be reported from two-sided tests at the 5% significance level.

5.2. Adjustments for multiplicity

No correction for multiple testing will be made

5.3. Analysis populations

All primary analyses (primary and secondary outcomes including safety outcomes) will be based on the intention-to-treat (ITT) principle. Participants will be analysed in the intervention group to which they were randomised, and all participants shall be included whether or not they received the allocated intervention. This is to avoid any potential bias in the analysis.

A per protocol analysis will be carried out as a sensitivity analysis and will only be performed for the primary outcome. Adherence and the per protocol group are defined in section 5.4.

Further details on the sensitivity analyses are given in section 9.10.

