5.4. Definition of adherence

Adherence to allocated intervention will be monitored by recording the administration of each of the four trial interventions and reasons why any of the trial interventions were not given. Blood banks will also monitor receipt of unused trial interventions upon return of the transport boxes.

We will define adherence, in the crystalloid arm of the trial, as the administration of at least one bolus of fluid. In the PHBP arm, adherence is defined as the administration of at least one unit of PRBC and one unit of LyoPlas. Non-adherence will be defined as the failure to administer at least one bolus of fluid in the crystalloid arm or the failure to administer at least one unit of PRBC and one unit of LyoPlas in the PHBP arm without clinical justification (e.g. deemed not to be needed clinically, or, patient arrives at ED before the second bolus can be administered, etc.).

The 'per protocol' population will include only those participants considered adherent to allocated intervention as described above.

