5.5. Handling protocol deviations

A protocol deviation is defined as a failure to adhere to the protocol such as errors in applying the inclusion/exclusion criteria, the incorrect intervention being given, incorrect data being collected or measured, follow-up visits outside the visit window or missed follow-up visits. We will apply a strict definition of the ITT principle and will include all participants as per the ITT population described in section 5.3 in the analysis in some form, regardless of deviation from the protocol.⁶ This does not include those participants who have specifically withdrawn consent for the use of their data in the first instance; however these outcomes will be explored as per other missing responses.

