9.8. Safety data

The number and percentage of participants experiencing any adverse events, serious adverse events (SAEs) and suspected unexpected serious adverse reactions (SUSARs) will be presented by intervention group. Statistical significance will be determined by a chi-squared test. The total number of SAEs in each group will also be given along with a descriptive table of the details of the events. A template for reporting this data is given in Appendix D8.

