9.10. Sensitivity analyses

Sensitivity analyses will be limited to the primary outcome and will consist of:

- Analysis adjusting for IDS and age, lactate, cardiac arrest and GCS at randomisation;
- Per-protocol analysis (population described in sections 5.3 and 5.4);
- An analysis to assess the effect of lactate timings Lactate clearance is calculated on measurements made at randomisation and 2 hours post-randomisation For this sensitivity analysis, time windows will be applied to the lactate measurements The lactate concentration at randomisation will only contribute to this analysis if the measurement was taken no more than 15 minutes (i.e. ≤15 minutes) before the PHEM team open the first transport box containing the allocated trial intervention The lactate concentration at 2 hours post randomisation will only contribute to this analysis if the measurement was taken within 30 minutes of the 2 hour assessment (i.e. between 1.5 and 2.5 hours post-randomisation) Lactate concentrations recorded outside these times will not be included in this sensitivity analysis
- An analysis to assess the effect of missing responses; missing responses will be simulated using a Markov chain Monte Carlo method (MCMC) to generate multiple datasets The imputation model will include the following variables: IDS, age, randomisation lactate, cardiac arrest, GCS, haemorrhage type, category of injury (penetrating, blunt, crush), heart rate, systolic blood pressure, and injury severity score Analysis will be then be performed on each set with the results combined using Rubin's rule to obtain a single set of results (treatment effect estimate and confidence intervals) Each component of the primary outcome will be imputed separately^{13,14}
- An analysis to assess the generalisability of the results by comparing baseline characteristics of those who are lost to follow-up or withdrawn from the trial with the trial

population

- An analysis to assess the generalisability of the results by comparing baseline characteristics of those who provide primary outcome data to those who do not provide primary outcome data

10. Analysis of sub-randomisations

Not Applicable

11. Health economic analysis

No health economic analysis is planned for this trial

12. Statistical software

Statistical analysis will be undertaken in the following statistical software packages: SAS v9.4 and RStan v2.19

13. References

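### Safety is tabulated only by randomised arm; a descriptive panel by trial product actually received should sit beside the ITT tables

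*SAP*

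**What the plan says.** Section 5.3 sets the population for every outcome: "All primary analyses (primary and secondary outcomes including safety outcomes) will be based on the intention-to-treat (ITT) principle". It adds that "all participants shall be included whether or not they received the allocated intervention", and gives avoidance of bias as the reason. One other population is defined, and its use is restricted: "A per protocol analysis will be carried out as a sensitivity analysis and will only be performed for the primary outcome". Section 9.10 repeats the limit for sensitivity analyses in general: "Sensitivity analyses will be limited to the primary outcome and will consist of", followed by a list with no safety item.

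Section 9.8 says that the counts of participants with adverse events, SAEs and SUSARs "will be presented by intervention group. Statistical significance will be determined by a chi-squared test". Appendix D8 has one column per randomised arm. ARDS and transfusion-related complications are in Appendix D7, also by arm.

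The plan allows for participants who receive nothing. Under sections 4.3 and 4.6 a participant is randomised when the first transport box is opened, which precedes any administration. Appendix D4 has rows for zero units. Section 5.4 names clinical reasons for not giving product and says that administration of each of the four trial interventions is recorded. The pilot rule in section 4.10 requires "at least one unit of PRBC and one unit of LyoPlas delivered to at least 80% of participants before reaching hospital" in the PHBP arm.

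**The concern.** Secondary objective VII asks whether PHBP raises the incidence of transfusion-related complications, ARDS in particular. That is a question about harm. For efficacy in a superiority trial, keeping untreated participants in their arm protects the randomised comparison and tends to be conservative. For a harm caused by the product, the same rule pulls the difference towards zero, because participants who never received the product cannot be harmed by it.

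No planned table has a PHBP column that means trial blood product was given. Appendix D4 will show how many received nothing, but it is not linked to safety events. A reader of the results could therefore see that some PHBP participants were untreated without seeing the event rates among those who were treated.

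**Working it through.** The point rests on no figure stated in the SAP. The sample size is used only for the arm size. The stated 219 per group reproduces (20% against 10%, two-sided 5%, 80% power, with continuity correction), and exact Fisher power at 219 per group is 81.2%. The final target of 490 at 1:1 gives 490 / 2 = 245 per arm.

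**Inputs**
- q, the share of the PHBP arm given no trial product: not in the SAP. Assumed range 5% to 20%. The upper end comes from the pilot rule: at least 80% must receive one unit of each product, so up to 20% may lack at least one. That 20% includes participants given only PRBC or only LyoPlas, who were exposed. It is therefore an upper guide to q, not an estimate.
- Harm rates: not in the SAP. Assumed 5% under crystalloid and 10% among PHBP participants given product, a true excess of 5.0 points.
- Assumption: untreated PHBP participants have the crystalloid-arm rate.

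**Formula**

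Observed PHBP rate = (1 − q) × treated rate + q × untreated rate. With the untreated rate equal to the crystalloid rate, the ITT risk difference = (1 − q) × the difference among the treated.

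**Results** (245 per arm, two-sided 5% test of two proportions)

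| q | PHBP rate in the ITT table | Risk difference | Relative risk | Power |
|---|---|---|---|---|
| 0 | 10.0% | 5.0 points | 2.00 | 56% |
| 5% | 0.95 × 10% + 0.05 × 5% = 9.75% | 4.75 points | 1.95 | 52% |
| 10% | 0.90 × 10% + 0.10 × 5% = 9.5% | 4.5 points | 1.90 | 48% |
| 20% | 0.80 × 10% + 0.20 × 5% = 9.0% | 4.0 points | 1.80 | 41% |

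The proportional loss in the risk difference equals q whatever harm rates are assumed. With 10% against 20%, for instance, the difference falls from 10 to 8 points at q = 20%, and power falls from 0.875 to 0.724.

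**Is the per-protocol set the remedy?** No. Section 5.4 says: "In the PHBP arm, adherence is defined as the administration of at least one unit of PRBC and one unit of LyoPlas". A participant given PRBC alone was exposed to a blood product but does not meet that definition. Its wording on clinical justification also leaves unclear whether some participants who received nothing count as adherent. A harm table needs groups defined by what was given.

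**The case against.** The strongest reply is that the plan makes an explicit, reasoned choice and follows it consistently. Several parts of that reply stand.

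- **ITT is a legitimate main safety analysis.** A reader might infer that the plan's safety analysis is invalid. It is not: the arms are comparable only as randomised.
- **No trial product does not mean no blood.** The SAP counts blood product receipt at 6, 12 and 24 hours after ED arrival. Appendix D7 assesses transfusion-related complications at 24 hours and ARDS within 7 days, so participants in either arm may be transfused in hospital before these outcomes are assessed. A panel by trial product received does not isolate exposure to blood.
- **Groups by receipt are confounded.** Section 5.4 gives lack of clinical need and early arrival at the ED as reasons for not giving product, and the footnote to Appendix D2a refers to deaths on scene or in transit. Receipt depends partly on severity and on surviving long enough. A reader might want harm conclusions to rest equally on both tables; this confounding rules that out.
- **Wrong-arm treatment is not a planned-for event.** Section 5.5 includes "the incorrect intervention being given" among examples of protocol deviations. A reader might infer that crossovers are expected, but this is a generic example with no frequency, and boxes are packed and sealed per allocation.
- **No upper bound for unseen events is planned.** A reader might contrast 1 − 0.05^(1/245) = 1.2% with 1 − 0.05^(1/196) = 1.5% for zero events. Appendix D8 reports counts, percentages and p-values only, so the plan states no such bound.
- **The analysis is unplanned, not forbidden.** Section 1 leaves later exploratory work free, and section 4.9 lets the DMC ask for other analyses.

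The argument that existing tables already cover the point does not stand. Appendix D4 gives units, D5 gives deviations, and section 9.8 and Appendix D8 describe or list SAEs. None gives event rates by product received.

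**Conclusion.** The point holds as a modest, inexpensive improvement. ITT is the only planned safety population, and untreated PHBP participants remain in every safety denominator. Under the stated assumption the harm difference is reduced by exactly the share given no trial product, so an assumed 5.0-point excess is reported as 4.75 to 4.0 points over an assumed 5% to 20%.

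The size is uncertain and may be small, because the SAP gives neither the share nor the harm rates and 20% is an upper guide. The direction applies to harms caused by the product. It is less certain if untreated participants differ in severity or die too early to be at risk of later events. The ITT tables should remain the primary safety presentation.

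**What to change.** In sections 5.3 and 9.8, keep the ITT safety tables as primary and add one supplementary descriptive panel:

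- **Events:** those in Appendix D8, plus ARDS and transfusion-related complications.
- **Groups:** any trial PRBC or LyoPlas unit given; trial saline only; no trial product.
- **Content:** n/N and percentage, without p-values.
- **Source:** the per-unit administration records described in section 5.4. Appendix D4 as laid out is not enough, because it has no blood-product counts under crystalloid.
- **Labelling:** state that the groups are not randomised and that receipt depends on severity and early survival. Report in-hospital blood product receipt for each group, since participants in all three may be transfused in hospital.

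Amend the restriction in section 5.3 so that this panel is allowed alongside the per-protocol analysis of the primary outcome. The cost is one table from data already recorded. The downside is that readers may over-interpret a confounded comparison, which the labelling and the absence of p-values are meant to limit.
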